4.5.2 Serious Adverse Events

Serious Adverse Event within 28 days from surgery. SAEs are collected in the following 6 categories:

- Death
- Immediately life-threatening
- In-patient hospitalisation or prolongation of existing hospitalisation
- Persistent or significant disability or incapacity
- Congenital abnormality or birth defect
- Important medical event that may jeopardise the subject or may require medical intervention to prevent one of the outcomes listed above.

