### 7.1.6 Definition of adverse events (AE)

An adverse event is the development of an undesirable medical condition or the deterioration of a pre-existing medical condition following or during exposure to a pharmaceutical product, whether or not considered causally related to the product. An undesirable medical condition can be symptoms (eg, nausea, chest pain), signs (eg, tachycardia, enlarged liver) or the abnormal results of an investigation (eg, laboratory findings, electrocardiogram). In clinical studies, an AE can include an undesirable medical condition occurring at any time, including run-in or washout periods, even if no study treatment has been administered.

The term AE is used to include both serious and non-serious AEs

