### 7.1.7 Definitions of serious adverse event (SAE)

A serious adverse event is an AE occurring during any study phase (i.e, run-in, treatment, wash-out, follow-up), that fulfils one or more of the following criteria:

- Results in death
- Is immediately life-threatening
- Requires in-patient hospitalisation or prolongation of existing hospitalisation
- Results in persistent or significant disability or incapacity
- Is a congenital abnormality or birth defect
- Is an important medical event that may jeopardise the subject or may require medical intervention to prevent one of the outcomes listed above.

For reporting purposes, any suspected transmission via a medicinal product of an infectious agent is also considered an SAE and is reported in an expedited manner. Any organism, virus or infectious particle (for example prion protein transmitting Transmissible Spongiform Encephalopathy), pathogenic or non-pathogenic, is considered an infectious agent.

For further guidance on the definition of a SAE, see Appendix B to the Clinical Study Protocol.

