#### **7.1.8.1 Variables**

The following variables will be recorded in the CRF for each AE; description of the AE, the date and time when the AE started and stopped, maximum intensity, whether the AE is serious or not, causality rating (yes or no), action taken with regard to investigational product, AE caused subject to discontinue study and outcome.

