### **10.2 Statistical analysis**

Analysis of data will be performed by a professional statistician. T-test for independent groups will be used for primary outcome. Descriptive statistics will be applied on the secondary outcomes including 30-days mortality, length of hospital stay and kidney function 5 days after start of infusion of Milrinone/Levosimendan. Additionally, clinical data (fluid balance, length of surgery, length of CPB, length of mechanical ventilation postoperatively, length of vasoactive therapy, number of vasoactive medications, total amount of infused vasoactive drugs, hemodynamic parameters) will be registered and analyzed. Univariate analyses will be used where needed. Multivariable regression analysis will be used to identify association between the occurrences of AKI (based on creatinine results) and the measured clinical variables.

Clinical Study Protocol  
Study Code: MiLe-1  
Drug Substance: Levosimendan  
EudraCT No: 013-003105-25  
Date

Other statistical methods might be used in an exploratory fashion but no formal inference will be made.

Safety and tolerability data will be summarized descriptively by treatment and presented in tabular and/or graphical form. All adverse event data will be listed individually and summarized using MedDRA terminology.

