5.6 Safety Analyses

5.6.1 *Adverse Events*

A summary of subjects reporting at least one of the following AEs will be presented in an overview table:

- Any AE
- Any SAE
- Any treatment-related AE (Definite, Probably and Possible)
- Any treatment-related SAE (Definite, Probably and Possible)
- Any AE leading to discontinuation
- Death

Summaries presenting n (%) of AEs and n (%) of subjects with at least one AE will be provided for:

- All AEs (includes all serious and non-serious AEs)
- All treatment-related AE (Definite, Probably and Possible)
- All SAEs
- All treatment-related SAE (Definite, Probably and Possible)

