8 LISTING OF TABLE, FIGURES AND LISTINGS

8.1 Listing of Tables

Table Number	Table Title
14.1.1	Patient Disposition and Data Sets Analyzed
14.1.2	Screening data (ITT Population)
14.1.3	Preoperative data (ITT Population)
14.1.4	Preoperative samples taken in OR from art and cvc line (ITT Population)
14.2	Concomitant treatments and medications by day (ITT Population)
14.3.1	AKI and corrected creatinine (ITT population)

STATISTISKA KONSULTGRUPPEN		Statistical Analysis Plan
Protocol: The prophylactic effect of Levosimendan in reducing acute kidney injury postoperatively in pediatric patients undergoing corrective heart surgery	Protocol No: MiLe-1	Version: 1.0 Page 17 of 17

14.3.2.1	Hemodynamic parameters by timepoint (ITT population)
14.3.2.2	Arterial blood gas test by timepoint (ITT population)
14.3.2.3	Rate of vasoactive drugs by timepoint (ITT population)
14.3.2.4	NGAL by timepoint (ITT population)
14.3.3.1	Fluid balance by timepoint (ITT population)
14.3.3.2	Morning lab results by timepoint (ITT population)
14.3.3.3	Morning Hemodynamics by timepoint (ITT population)
14.3.3.4	Blood gas at 6 am by timepoint (ITT population)
14.3.3.5	Rate of vasoactive drugs at 06:00 am by timepoint (ITT population)
14.3.3.6	Cardiopulmonary bypass and use of cortisone in OR by timepoint (ITT population)
14.3.3.7	Other parameters by timepoint (ITT population)
14.4.1	Univariable and multivariable analyses of AKI (ITT population)
14.4.2	Correlation analyses (ITT population)
14.5.1	Summary of Adverse Events (Safety Population)
14.5.2	All AEs (includes all serious and non-serious AEs) (Safety Population)
14.5.3	All treatment-related AE (Definite, Probably and Possible) (Safety Population)
14.5.4	All SAEs (Safety Population)
14.5.5	All treatment-related SAE (Definite, Probably and Possible) (Safety Population)

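### The SAP classifies serious adverse events only by seriousness criterion and plans no event terms, MedDRA coding or formal listings, although the protocol commits to a MedDRA summary and individual listing

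*SAP*

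**What the plan says.** **SAP.** Section 4.5.2 covers SAEs up to 28 days after surgery and states that "SAEs are collected in the following 6 categories". The six are death, immediate threat to life, hospital admission or a longer stay, lasting disability, congenital abnormality, and other important medical events. Section 5.6.1 states "Summaries presenting n (%) of AEs and n (%) of subjects with at least one AE will be provided for" and names four groups: all AEs, treatment-related AEs, all SAEs and treatment-related SAEs. In section 8.1 the SAE tables are 14.5.4, whose title begins "All SAEs (Safety Population", and 14.5.5 for treatment-related SAEs. No row layout is given for either. Section 8.3 plans no formal listings and sends the analysis data to the sponsor in Excel. Section 7, meant for changes from the protocol, holds only an instruction on how to fill it in.

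**Protocol.** Section 10.2, like the synopsis, states "All adverse event data will be listed individually and summarized using MedDRA terminology". Section 7.1.6 adds "The term AE is used to include both serious and non-serious AEs". Section 7.1.8.1 states "The following variables will be recorded in the CRF for each AE; description of the AE", followed by timing, intensity, seriousness, causality, action taken and outcome.

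**The concern.** A seriousness criterion records why an event had to be reported as serious. It does not record whether the event was hypotension, an arrhythmia, a bleed or a seizure. The trial compares two vasodilating inotropes, and Protocol 7.1.4 names hypotension and arrhythmias as reported reactions of both. The useful safety question is therefore which kinds of serious event occurred on which drug. A table whose only rows are seriousness criteria does not answer it. Two arms could look alike in such a table while their serious events differed in kind.

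**Working it through.** No figure in the plan depends on this point, so the check is a comparison of texts.

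**1. What the six categories are.** The list in SAP 4.5.2 matches the list that defines an SAE in Protocol 7.1.7, six items out of six. The protocol describes an SAE as an event "that fulfils one or more of the following criteria", so the categories can overlap. The SAP gives no rule for an event that meets two.

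**2. Whether the MedDRA commitment covers SAEs.** It does. Protocol 10.2 speaks of all adverse event data, and 7.1.6 makes serious events part of that term.

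**3. Whether the SAP supplies event terms anywhere else.**

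| Item | Protocol | SAP |
|---|---|---|
| Event description recorded | Yes, for each AE (7.1.8.1) | Not mentioned for SAEs |
| Coding | MedDRA (10.2) | None mentioned in the supplied text |
| SAE grouping | Via MedDRA terms | Six seriousness criteria (4.5.2) |
| Individual listing | Yes (10.2) | No formal listings (8.3) |
| Change declared | n/a | None (section 7) |

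SAP 4.5.1 does group AEs by kind: heart rate above 200/min, arrhythmia, inotropic score above 20, low thrombocytes and hypokalaemia. Section 4.5.2 has no equivalent for SAEs.

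**4. Whether an amendment explains it.** The amendment that introduced the five AE criteria gives as its reason that AEs lacked a definition while SAEs already had a good one. It does not withdraw MedDRA terms for SAEs.

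**5. What is reported by arm elsewhere.** SAP 5.1 summarises all baseline, efficacy and safety variables by treatment group.

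| Domain | Where in the SAP | Limit |
|---|---|---|
| Kidney | AKI (4.4.1); AKI stage and dialysis (4.4.3, 4.2.2) | To 96 hours or postoperative day 4 |
| Rhythm | AE category (4.5.1); rhythm and pacing (4.4.2, 4.4.3) | Fixed time points, to day 4 |
| Blood pressure | Mean arterial pressure and inotropic score (4.4.2, 4.4.3) | Fixed time points, to day 4; hypotension is not one of the five AE categories |
| Bleeding | Transfusions (4.2.1, 4.2.2); thrombocytes (4.4.3, 4.5.1) | Indirect measures, to day 4 |

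These are measurements and treatments in the first days. SAEs are collected to 28 days. Table 14.5.2, which covers serious and non-serious AEs together, could label a serious event that falls in one of the five AE categories. Any other serious event has no planned label.

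**6. What the layout could conceal.** The documents give no expected SAE rate, so the following counts are purely hypothetical. Take the planned 35 infants per arm and two kinds of serious event, both recorded under the same seriousness criterion and in different infants. Let kind A occur in 6/35 on levosimendan and 0/35 on milrinone, and kind B in 0/35 and 6/35.

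- Row shown for levosimendan: 6 + 0 = 6, and 6/35 = 17.1%.
- Row shown for milrinone: 0 + 6 = 6, and 6/35 = 17.1%.

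The row is identical in the two arms although both kinds of event differ. No p-value is attached, because Protocol 10.2 makes the safety analysis descriptive.

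**The case against.** The strongest reply is that SAP 4.5.2 describes how SAEs are collected, not how they are tabulated. The layouts of Tables 14.5.4 and 14.5.5 are not shown, and the SAP is silent on MedDRA rather than opposed to it. This stands. A reader might infer that the SAE tables are bound to be uninformative, or that a drug-specific difference must go unseen. The documents support neither reading. They show that 4.5.2 is the only SAE classification the SAP offers, so a programmer working from the SAP alone has nothing else to use.

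A second reply is that the obvious signals are covered elsewhere by arm. This is partly right, as step 5 shows, and deaths would be visible as a count. But those data stop at about day 4 and are not SAEs, and a death count does not give the cause.

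A third reply is that nothing is lost from the data. Descriptions are recorded, data go to the sponsor in Excel, and Protocol 7.1.13 has each infant with an SAE described in the study report with the code broken. In a trial of 70 infants those cases could be counted by hand. That is true, and it is why the fix is cheap. However, grouping events once allocation is known leaves room for choice, and case descriptions are not a planned comparison.

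The overlap between criteria and the congenital-abnormality category carry little weight. Both come from the protocol's own definition, and neither distorts the number of infants with at least one SAE.

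**Conclusion.** The point holds in a limited form. The SAP gives a less informative SAE classification than the protocol promises, drops the formal listing, and does not declare either departure. If the SAE tables follow 4.5.2, they will not describe by arm what the serious events were. The gap matters most for events outside the five AE categories and for events after the first postoperative days.

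This rests on two assumptions: that the undisplayed table layouts follow the only classification given, and that no coding instruction exists outside the supplied SAP text. The size cannot be expressed as a number, since no SAE rate is stated. The primary efficacy analysis is untouched. The change should be made before database lock, because it restores a protocol commitment at little cost.

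**What to change.** In SAP 4.5.2 and 5.6.1:

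- State that each recorded SAE description is coded to MedDRA before the treatment groups are revealed to the analysts. Because Protocol 7.1.13 has the code broken when an SAE occurs, the coder should work from descriptions with the allocation removed.
- Lay out Tables 14.5.4 and 14.5.5 by System Organ Class and Preferred Term, with numbers of infants and of events in each arm, descriptively and without tests.
- Keep the six seriousness criteria as a second breakdown, marked as non-exclusive.

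In SAP 8.3, restore an individual SAE listing. If the sponsor prefers not to do any of this, SAP section 7 should record the departure from Protocol 10.2 and justify it.

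The cost is coding time for the SAEs in 70 infants, a revised layout for two tables, and one listing. No new data collection is needed if descriptions were recorded as Protocol 7.1.8.1 requires.

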5 STATISTICAL METHODOLOGY

5.1 General Methodology

All baseline, efficacy and safety variables will be summarized by treatment group. Continuous variables will be presented with mean, standard deviation (SD), Median, minimum, maximum and number. Categorical variables will be presented as number and percentage (%).

All tests will be two-tailed and conducted at 0.05 significance level. All analyses will be performed by using SAS® v9.4 (Cary, NC).

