4.4.2 Secondary endpoints post-op

Post-op will be measured at 5-10 min before CBP (T0), 5-10 min after CBP (T1), 2h after weaning from CPB (T2), 6h after weaning from CPB (T3), 8-12 hours post CBP-weaning, 24h after weaning from CPB (T4), 4 days after weaning from CPB (T5) (all variables are not

STATISTISKA KONSULTGRUPPEN		Statistical Analysis Plan	
Protocol: The prophylactic effect of Levosimendan in reducing acute kidney injury postoperatively in pediatric patients undergoing corrective heart surgery	Protocol No: MiLe-1	Version: 1.0	Page 11 of 17

present at all timepoints). Changes from T0 will be calculated for all variables where applicable.

Hemodynamic parameters measured at T0-T4 (not T5) and additionally at 8-12 hours post CPB-weaning

- Heart rate (BPM)
- Heart rhythm (SR/NR/Other)
- Pacing (Yes/No) (Missing on T0)
- Mean BP M A P (mmHg)
- CVP (mmHg)
- Central venous saturation (%)
- NIRS brain (%)
- NIRS kidney (%)
- Ventilated (Yes/No)

Arterial blood gas test

- pH
- sO₂ (%)
- cLac (mmol/L)
- Hb (g/L)
- Hct

Rate of vasoactive drugs

- Inotropic score
- 2 ml blood sample in ice taken (YES/NO)

NGAL

- NGAL plasma

T5

- T5 taken at postoperative day nr (2-7)

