5.5.2 Secondary Efficacy Analyses

Complementary analyses of the primary analysis will be made up to 72 hours and also one analysis up to 96 hours in the same fashion as the primary analysis.

Secondary variables will be presented at each timepoint and changes from baseline (screening, pre-op) will be calculated where applicable. T-test for independent groups will be used for secondary continuous outcomes if the data not is clearly non-normal distributed. If baseline values differs between groups adjustment for baseline values will be made using a covariance analysis will be made. If the outcome is clearly non normal distributed Fishers non parametric permutation test will be used instead of t-test.

Categorical (no/yes) variables will be analysed between groups by using Fisher exact test.

Univariable and multivariable logistic regression analysis will be used to identify association between the occurrences of AKI (based on creatinine results) and the measured clinical variables.

STATISTISKA KONSULTGRUPPEN		Statistical Analysis Plan
Protocol: The prophylactic effect of Levosimendan in reducing acute kidney injury postoperatively in pediatric patients undergoing corrective heart surgery	Protocol No: MiLe-1	Version: 1.0
		Page 16 of 17

5.5.3 *Exploratory Efficacy Analyses*

Selected correlation analyses will be performed between secondary variables/outcomes.

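### The SAP tests secondary outcomes at 0.05 without multiplicity control, label or confidence intervals, where the protocol planned descriptive statistics, and the change is not declared

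*SAP*

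**What the plan says.** Protocol 10.2 gives an independent-groups t-test to the primary outcome. For the rest it says "Descriptive statistics will be applied on the secondary outcomes", naming 30-day mortality, hospital stay and day-5 kidney function. It adds that a list of clinical data will be recorded and analysed, allows univariate analyses if needed, and plans a multivariable regression of AKI. The synopsis places that clinical list under descriptive statistics as well. The words "no formal inference will be made" close a separate sentence in 10.2 about other methods used for exploration.

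SAP 5.1 states "All tests will be two-tailed and conducted at 0.05 significance level". Its general methodology lists group summary statistics only, and no section of the SAP specifies a confidence interval.

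SAP 5.5.2 states "Secondary variables will be presented at each timepoint and changes from baseline (screening, pre-op) will be calculated where applicable", then "T-test for independent groups will be used for secondary continuous outcomes if the data not is clearly non-normal distributed". It substitutes a permutation test for clearly non-normal data and covariance analysis where baseline differs. It also states "Categorical (no/yes) variables will be analysed between groups by using Fisher exact test". The separate exploratory section, 5.5.3, covers correlations only. No secondary endpoint is singled out and no testing order is given. SAP section 7 contains an instruction to list changes but lists none.

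**The concern.** Moving from description to testing at a fixed level changes what a secondary result can be taken to mean. A statistician may defend either approach, but the move should be declared and the status of the p-values stated. Neither is done here.

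The secondary list is long, and much of it is repeated over time. It also contains several overlapping kidney measures: creatinine, two versions of corrected creatinine, cystatin C, three eGFRs and AKI stage. If the AKI test in SAP 5.5.1 is not significant, readers will turn to these tables. A few chance results among related kidney variables could then be taken as evidence of renal protection. Without intervals, a reader also cannot see how large or how imprecise a difference is.

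**Working it through.** **The plan's own figures.** The documents give no number of tests and no overall error rate, so there is no such figure to reproduce. The only design figure is 35 per group, for a 20% creatinine reduction at 80% power. No SD is given, so it cannot be checked. It implies a coefficient of variation of 0.20 / [(1.960 + 0.842) × √(2/35)] = 0.299. Nothing below depends on it.

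**Assumption.** One test per variable and post-baseline time point. SAP 5.5.2 implies this by presenting variables at each time point, but its test sentences name no time points.

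**Count from SAP 4.4.2.** The time grid is "Hemodynamic parameters measured at T0-T4 (not T5) and additionally at 8-12 hours post CPB-weaning", which gives five times after T0.

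| Block | Cells |
|---|---|
| Haemodynamics, 9 × 5 | 45 |
| Arterial gas, 5 × 5 | 25 |
| Inotropic score | 5 |
| NGAL, T1 to T5 | 5 |
| Subtotal | 80 |

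**Count from SAP 4.4.3 (days 1 to 4).**

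| Block | Cells |
|---|---|
| Fluid balance, urine, weight, %FO (16); cumulative %FO (3); peritoneal dialysis (2) | 21 |
| Seven laboratory values × 4 (28); two corrected creatinines × 3 (6); AKI at 72 and 96 h (2); AKI stage (3); cystatin C, urea and three eGFRs × 4 (20) | 59 |
| Morning haemodynamics (20); inotropic score (4); morning gas, 7 × 4 (28) | 52 |
| Bypass and cortisone (4); other parameters (5) | 9 |
| Subtotal | 141 |

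Total: 80 + 141 = 221, of which 186 are continuous and 35 categorical.

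**Expected chance findings.** With m tests of exact size 0.05 and no true differences, the expected number is 0.05 × m. Correlation between tests does not alter this mean.

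| Counting rule | m | 0.05 × m |
|---|---|---|
| Main count | 221 | 11.05 |
| Less 16 doubtful cells (uncertain time points; surgery, risk-score and dialysis items) | 205 | 10.25 |
| Also less 23 derived-variable cells | 182 | 9.1 |
| Main count plus 15 T0 cells | 236 | 11.8 |
| Main count plus 163 change scores | 384 | 19.2 |

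**Fisher's test is conservative.** At 35 v 35 its true size is 0.0001 to 0.0278 for event rates of 2% to 50%. The main count then gives 186 × 0.05 + 35 × 0.0001 = 9.3 at the low end and 186 × 0.05 + 35 × 0.0278 = 10.3 at the high end.

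**Spread.** Under independence, the chance of at least one false positive in 221 tests is 1 − 0.95^221, which exceeds 0.999. In a simulation of 55 variables at four times, with an assumed within-variable correlation of 0.6, the mean stayed near 11 and the 5th to 95th percentile range was 5 to 18. If all 221 tests shared a correlation of 0.6, the mean was still about 11, but the median fell to 3, the 95th percentile rose to 53, and the chance of at least one was 0.78.

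**The case against.** The confirmatory claim rests on one prespecified test in SAP 5.5.1. The secondary tests do not alter its error rate, and the SAP attaches no claim to any of them. That stands, and it limits the point to how the secondary results are read.

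The count can also be challenged. Bypass time, cross-clamp time, temperature and the risk scores largely describe surgery or case mix. SAP 4.4.2 says that not every variable is measured at every time. T0 precedes study drug, so T0 differences are baseline differences. Fisher's test is assigned to yes/no variables, so three-level rhythm (9 cells) and four-level AKI stage (3 cells) have no named test. Dropping those 12 leaves 221 − 12 = 209 cells and 10.45 expected. The 182-cell count already omits AKI stage, so dropping rhythm leaves 173 and 8.65. These objections justify a range instead of a single figure, but the expected number stays near 9 or above before allowing for Fisher's conservatism.

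A reader might infer that the protocol forbids formal inference on secondary outcomes and that the SAP reverses this. The text does not go that far. In protocol 10.2 the no-inference clause governs other, exploratory methods, and univariate analyses are allowed. Nor does 10.2 call any p-value nominal. The support comes from the descriptive-statistics sentence alone.

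Finally, confining testing strictly to the primary endpoint would remove the test of second-day creatinine. That is the variable both documents use to size the trial and the one the protocol assigned a t-test. This objection is sound, and the fix allows for it.

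**Conclusion.** The point holds in limited form. The SAP moves secondary outcomes from description to testing at two-sided 0.05, without multiplicity control, a nominal or exploratory label, or confidence intervals, and does not declare the move. If each post-baseline time point is tested, there are about 180 to 240 comparisons, and about 9 to 12 nominally significant results are expected by chance. That expectation assumes no difference between the drugs on any variable and tests of exact size 0.05. Any real effect lowers it, and change scores would raise the main count to 384 tests and 19.2 expected.

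Three stronger readings are not supported. The number of tests is not securely well above 200. Eleven false findings are not a prediction, because the figure is an average under a global null with a wide spread. And the secondary tests do not undermine the primary result. The matter should be corrected before analysis because it governs the interpretation of almost everything outside the primary test.

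**What to change.** In SAP 5.1 and 5.5.2:

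- Reserve the 0.05 decision for the primary endpoint analysed in 5.5.1.
- Keep the t-test of second-postoperative-day serum creatinine as the one named secondary test, and state how its result will be interpreted alongside the primary. SAP 1.1 still names this variable as primary, so its status must be made consistent.
- For every other secondary outcome, report the treatment difference with a 95% CI. State that any p-value is nominal, unadjusted for multiplicity and supports no confirmatory claim.
- State whether comparisons are made at each time point, on change scores, or both.

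Record the departure from protocol 10.2 in SAP section 7.

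This needs no new data or patients, only SAP wording and interval output in the tables. The cost is that no secondary result other than the named creatinine test can be called significant.
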